## 7.2 CONCOMITANT DISEASES AND MEDICATION

Concomitant diseases will be coded according to the most recent version of MedDRA. Concomitant medication will be coded according to the most recent version of the World Health Organisation – Drug Dictionary.

Only descriptive statistics are planned for this section of the CTR.

## 7.4 PRIMARY ENDPOINT

**CTP Section 7.3.1:** *Image analysis will be used to generate the outcome parameter for the PET data (proportional to the target availability at each PET scan), using the PET emission and the metabolite corrected arterial plasma input function, within an appropriate kinetic model. Tissue time-activity curves (TACs) for each region of interest (ROI) will be analysed together with arterial blood data, processed to generate metabolite-corrected arterial plasma input function curves. Kinetic modelling techniques will then be applied to the input function and TAC data to estimate parameters relating to the level of target availability for each PET scan. For scans following 14, 28 or 42 days of dosing with BI 1467335, fractional occupancy values will be generated for each post-dose PET scan by comparing the outcome parameters for baseline and post-dose scans for a subject (primary endpoint).*

### 7.4.1 Primary analysis of the primary endpoint

The primary endpoint will be analyzed based on the PETs.

Individual line plots of reduction of MAO-B availability over time by dose group and median reduction of MAO-B availability by dose group over time will be created. Descriptive statistics will be provided.

#### 7.4.2 Sensitivity analysis, subgroup analysis, exploratory analysis of the primary endpoints

An Emax model will be fitted for plasma concentration against % reduction of MAO-B availability. The analysis will be performed on the PKS.

The model is defined as follows:

$$\% \text{ reduction} = E0 + Emax * \text{Concentration}^{**N} / (\text{Concentration}^{**N} + ED50^{**N})$$
,  
with E0 (basal effect) being set to 0. Parameters to be estimated are Emax (maximum effect), ED50 (concentration which produces half of Emax) and N (Hill factor).

SAS procedure PROC NLIN will be used for this analysis.

```
PROC NLIN DATA = indata METHOD = marquardt;
PARAMETERS IMAX = imax.-5 to imax.+5 by 2.5
          IC50 = ic50.*0.8 to ic50.*1.2 by ic50.*0.1.
          HILL = 1 to 10 by 3;
MODEL reduct = 0+(IMAX*conc**HILL)/(IC50**HILL+conc**HILL);
RUN;
```

Starting values will use a range for IMAX, IC50 and HILL. The imax starting value will be estimated as the maximum value of MAO-B % reduction across all time points and subjects. This value will be increased and decreased by an absolute 2.5 twice to both sides to get a range of starting values (values above 100 will be set to 100). The HILL factor will be set to 1, 4, 7, and 10. The ic50 starting value will be estimated as the median plasma concentration across all time points and for all subjects. This value will be decreased and increased by a relative 10% twice to both sides to come to an adequate starting value range (values less than 0 will be set to 0).

The Emax model will also be presented graphically.

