1.3 RATIONALE FOR PERFORMING THE TRIAL

In vitro data for BI 1467335 indicate an irreversible inhibition of MAO-B activity (see [Section 1.2](#)). Currently, there is no clinical information regarding brain penetration of BI 1467335 in humans, therefore the clinical relevance of this finding remains open and will be explored with the planned study.

This trial is intended to identify and quantify MAO-B inhibition in the brain in healthy male subjects following multiple oral administration of BI 1467335. MAO-B inhibition will be assessed by PET imaging using [¹¹C]-L-deprenyl-D2 as an established PET ligand. PET imaging will be conducted on predose, Day 14 and Day 28 during a 4-week treatment period with oral doses of once daily 10 mg of BI 1467335 and on predose, Day 28 and Day 42 during a 6-week treatment period with oral doses of once daily 3 mg of BI 1467335. The 10 mg dose group will be investigated first and, in the event no MAO-B inhibition is seen in this dose group, the study will be considered complete and no further investigation with a lower dose (3 mg dose group) will be conducted.

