3. DESCRIPTION OF DESIGN AND TRIAL POPULATION

3.1 OVERALL TRIAL DESIGN AND PLAN

The study will be performed as a non-randomised, open-label, parallel-group, multiple dose trial in healthy male subjects in order to investigate the effect of multiple oral doses of 10 mg BI 1467335 administered once daily over 28 days and of 3 mg BI 1467335 administered once daily over 42 days on MAO-B activity in the brain. The MAO-B activity will be assessed by means of a dynamic PET scan using [¹¹C]-L-deprenyl-D2 PET as tracer. PET scans will be conducted predose and on Day 28 for both dose groups. An additional PET scan will be conducted on Day 14 in the 10 mg dose group and on Day 42 in the 3 mg dose group. On these days, subjects will be injected with the radiotracer and subsequently undergo dynamic PET scans. In addition to PET scan, MAO-B activity will be also measured in platelet rich plasma.

For the 10 mg dose group, subjects will be hospitalised from Day -1 to Day 29.

For the 3 mg dose group, subject will be hospitalised from Day -1 to Day 43. The subjects will be allowed to leave the clinical unit in the afternoon on Day 7 and Day 14.

The 10 mg dose group will be investigated first. In case no MAO-B inhibition is seen in this dose group, the 3 mg dose group will not be further investigated.

The oral treatments will consist of either two 5 mg or three 1 mg film-coated tablets (dose strength based on free base) for subjects dosed with 10 mg and 3 mg BI 1467335, respectively. The treatments will be administered once daily for 28 days for the 10 mg dose groups and once daily for 42 days for the 3 mg dose groups. The subjects willing to participate can choose convenient visit dates on a first-come, first-served basis: as soon as 5 subjects have been allocated to 1 of the 2 dose groups, the following subjects will be allocated to the other dose group. For details, refer to [Section 4.1](#).

An overview of all relevant trial activities is provided in the [Flow Chart](#). For visit schedule and details of trial procedures at selected visits, refer to [Sections 6.1](#) and [6.2](#), respectively.

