3.2 DISCUSSION OF TRIAL DESIGN, INCLUDING THE CHOICE OF CONTROL GROUP

The doses selected for this study, 10 mg BI 1467335 q.d. (2 film-coated tablets of 5 mg dose strength) and 3 mg BI 1467335 q.d. (3 film-coated tablets of 1 mg dose strength), have been used in healthy volunteers and shown to be well tolerated. The predose measurement will be used as a baseline, so no placebo dose is required in this study.

The planned dosing duration of 28 days for the 10 mg dose group and 42 days for the 3 mg dose group is long enough to reliably achieve steady-state drug exposures and to exclude any transient effects.

Due to the time dependent non-linear kinetics of BI 1467335, systemic exposures on Day 28 and Day 42 cannot be predicted from Day 1 kinetics (IB [[c04751792](#)]). Therefore the MAO-B inhibition in the brain will be determined on Day 28 and Day 42 after start of treatment

Proprietary confidential information © 2019 Boehringer Ingelheim International GmbH or one or more of its affiliated companies

with 10 mg and 3 mg BI 1467335, respectively, and compared to the individual baseline value to investigate the maximum inhibition. The *in vitro* data suggested an irreversible inhibition, which could potentially accumulate over time following multiple dosing and with the increase in exposure observed over time which characterizes BI 1467335 kinetics. The investigation on Day 14 for the 10 mg dose group and on Day 28 for the 3 mg dose group will evaluate whether the MAO-B inhibition reaches its maximum over the treatment duration and is maintained regardless of the increase in BI 1467335 systemic exposure. The 10 mg dose group will be investigated first. In the event no MAO-B inhibition is seen following the administration of 10 mg BI 1467335 daily over 28 days, the study will be considered as complete and no further investigation with a lower dose (3 mg) will be conducted.

[¹¹C]-L-deprenyl-D2 is a PET radioligand used for measurement of the MAO-B activity in the brain. This radioligand has been used for several PET studies to evaluate MAO-B inhibition in the brain in healthy subjects and is unlikely to exhibit any detectable isotope effects (see [Section 1.4](#)).

Because of the exposure with radioligands the study will only include male subjects.

The open-label treatment is not expected to bias results, since the study endpoints are derived from medical procedures and laboratory assessments with an unlikely relevant impact by subjective factors.

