7.3.1 Primary endpoint analyses

Image analysis will be used to generate the outcome parameter for the PET data (proportional to the target availability at each PET scan), using the PET emission and the metabolite corrected arterial plasma input function, within an appropriate kinetic model. Tissue time-activity curves (TACs) for each region of interest (ROI) will be analysed together with arterial blood data, processed to generate metabolite-corrected arterial plasma input function curves. Kinetic modelling techniques will then be applied to the input function and TAC data to estimate parameters relating to the level of target availability for each PET scan. For scans

Proprietary confidential information © 2019 Boehringer Ingelheim International GmbH or one or more of its affiliated companies

following 14, 28 or 42 days of dosing with BI 1467335, fractional occupancy values will be generated for each post-dose PET scan by comparing the outcome parameters for baseline and post-dose scans for a subject (primary endpoint). In addition to the individual values, descriptive statistics per dose group will be provided.

The occupancy data will be related to the plasma concentration of BI 1467335 at the time of the PET scan.

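### The exploratory Emax fit carries no dosing duration, so its ED50 and Hill factor may mix duration with concentration if MAO-B inhibition has not plateaued by the earlier scans

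*SAP*

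**What the plan says.** SAP 7.4.2, under sensitivity, subgroup and exploratory analyses, states that "An Emax model will be fitted for plasma concentration against % reduction of MAO-B availability". The basal effect is fixed at zero, and three parameters are estimated: Emax, ED50 and the Hill factor. The PROC NLIN call has concentration as its only explanatory variable. It has no term for dosing day, dose group or subject.

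Pooling over scan days is not stated outright for the fit. It is implied by the code, which selects no day, and by the text on starting values: "The imax starting value will be estimated as the maximum value of MAO-B % reduction across all time points and subjects" and "The ic50 starting value will be estimated as the median plasma concentration across all time points and for all subjects".

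The exposure measure comes from protocol 7.3.1: "The occupancy data will be related to the plasma concentration of BI 1467335 at the time of the PET scan".

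On timing, protocol 3.1 says "PET scans will be conducted predose and on Day 28 for both dose groups". The remaining scan is on Day 14 in the 10 mg group and on Day 42 in the 3 mg group.

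On mechanism, protocol 1.3 says that in vitro data "indicate an irreversible inhibition of MAO-B activity". Protocol 3.2 adds that this is an inhibition "which could potentially accumulate over time following multiple dosing", while systemic exposure also rises with time. The same section gives the earlier scan (Day 14 at 10 mg, Day 28 at 3 mg) the task of showing whether inhibition has already reached its maximum.

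**The concern.** A curve of this form assumes that a given concentration produces the same inhibition on any scan day. For an irreversible inhibitor, the enzyme left at a scan depends on past exposure and on how fast new enzyme is made, so the same concentration can give less inhibition after 14 days than after 42. The protocol treats plateau as an open question, whereas the model takes it as settled.

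The scan schedule adds to this. The shortest dosing occurs only at the high dose and the longest only at the low dose, so part of any duration effect can be absorbed into the shape of the concentration curve. This is the only concentration-response model in the public text of the SAP, and it will be plotted. A reader would naturally take its ED50 as potency.

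**Working it through.** The documents give no figure to reproduce: there is no power or precision calculation (protocol 7.7) and no MAO-B turnover rate. The check is therefore a what-if.

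**Inputs from the documents.** 5 subjects per group (protocol 7.7), with scans on Days 14 and 28 at 10 mg and Days 28 and 42 at 3 mg (protocol 3.1). That gives 5×2 + 5×2 = 20 post-dose scans, of which 5 + 5 = 10 are on Day 28. The fitted model is that of SAP 7.4.2.

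**Assumptions not in the documents.** Enzyme turnover half-life h of 5 to 40 days. 3 mg to 10 mg concentration ratio of 0.1 or 0.3. Typical 10 mg concentration of 1, 3.3 or 10 times the steady-state EC50. Between-subject log-SD of 0.4. Exposure either constant or, for the 3.3 and 10 cases, rising from 30% of its final level with a 14-day time constant. True Hill factor 1, no noise.

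**Step 1, one concentration on different days.** For an irreversible inhibitor at constant concentration, with u = C/EC50 and k = ln 2/h,

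reduction on day t = 100 × u/(1+u) × [1 − exp(−k(1+u)t)].

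With h = 20, k = 0.0347. At u = 1:
- Day 14: 50 × (1 − exp(−0.970)) = 31%
- Day 28: 50 × (1 − exp(−1.941)) = 43%
- Day 42: 50 × (1 − exp(−2.911)) = 47%

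The spread shrinks as concentration rises. With the same h, u = 3.33 gives 67.5%, 75.8% and 76.8%, and u = 10 gives 90.5%, 90.9% and 90.9%.

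Setting the reduction to 50% and solving for u gives the time-specific ED50 as a multiple of the steady-state EC50:

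| h (days) | Day 14 | Day 28 | Day 42 |
|---|---|---|---|
| 5 | 1.04 | 1.00 | 1.00 |
| 10 | 1.28 | 1.04 | 1.01 |
| 20 | 1.93 | 1.28 | 1.10 |
| 40 | 3.33 | 1.93 | 1.49 |

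**Step 2, how far day and concentration are tied.** In the 20-scan layout the correlation of dosing day with log concentration is −0.62 to −0.68 with constant exposure and −0.53 to −0.64 with rising exposure. It is partial because Day 28 is shared. Within a subject, rising exposure pulls the other way.

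**Step 3, fit the SAP curve to the generated data** (least squares, Emax capped at 100), pooled and on Day 28 only. ED50 is relative to the steady-state EC50:

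| h (days) | Pooled, 20 scans | Day 28, 10 scans | Pooled ÷ Day 28 |
|---|---|---|---|
| 5 | 1.00–1.06 | 0.99–1.03 | 0.99–1.03 |
| 10 | 1.01–1.21 | 1.00–1.13 | 0.95–1.1 |
| 20 | 1.12–1.76 | 1.23–1.50 | 0.86–1.35 |
| 40 | 1.56–3.53 | 1.82–2.38 | 0.81–1.75 |

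The last column is taken scenario by scenario. At 40 days, for example, the ends are 1.56/1.93 = 0.81 and 3.53/2.02 = 1.75.

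**Step 4, Hill factor** (constant exposure). At 20 days the pooled value is 0.89–1.11 against 1.10–1.23 for Day 28. At 40 days it is 0.82–1.14 against 1.11–1.41. The pooled curve is flatter than the Day 28 curve in every scenario at these half-lives, but it is not further from the true value of 1.

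**The case against.** The strongest reply is that nothing here is shown to go wrong. Irreversibility rests on in vitro data, and the protocol says only that inhibition could accumulate. A reader might infer that accumulation is expected and that the ED50 is therefore biased. The documents do not support that: no turnover rate is given, and at 5 days the distortion vanishes. Protocol 3.2 also regards the full 28 or 42 days as long enough to rule out transient effects. That point stands for the last scan in each group, but it says nothing about Day 14 at 10 mg or Day 28 at 3 mg, which also enter the fit.

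A reader might also infer a fixed direction, with low concentrations looking too potent and high ones too weak. Against steady state the pooled ED50 is too high when turnover is slow. Against the Day 28 curve, however, the shift goes either way, and the time effect is smallest where concentrations are highest.

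A third tempting step is to make Day 28 the main fit. That is a trade-off, not a clear gain. It leaves three parameters on 10 points in two dose clusters. It still overstates the steady-state EC50 when turnover is slow (1.82–2.38 at 40 days). When noise was added to the simulated data, its ED50 error was larger than the pooled fit's at a 5-day half-life and the comparison was mixed at 20 to 40 days.

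Finally, the consequence is limited. The trial is descriptive (protocol 7.2), and SAP 7.4.1 already plots individual and median reduction over time by dose group, so drift would be visible. It would not be corrected in the curve, though, and the SAP does not say how the ED50 is to be read.

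**Conclusion.** The concern holds conditionally. The model is free of time, scan day is partly tied to dose by design, and the protocol itself leaves plateau open. If inhibition has plateaued by the earlier scans, the pooled fit is sound. If it has not, the pooled ED50 and Hill factor mix duration with concentration. Under the assumptions above the pooled ED50 is at most 1.06 times the steady-state value at a 5-day half-life, and about 1.1 to 3.5 times at 20 to 40 days. These figures rest on an assumed turnover rate, potency and exposure pattern, and they show a range of possibilities, not an estimate for this drug.

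The primary endpoint, its descriptive analysis and the decision to proceed to 3 mg do not depend on this fit. What is at risk is a potency reading of the ED50. Some SAP sections are absent from the public text, so a safeguard there cannot be excluded.

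**What to change.** In SAP 7.4.2:

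- State that the main exploratory fit pools all post-dose scans, and keep it.
- Add a sensitivity fit on the Day 28 scans of both dose groups, the one duration they share, and report it beside the pooled fit.
- Mark points by scan day and dose group on the Emax plot.
- State that the pooled ED50 will not be interpreted as potency unless the two fits agree, and label the Day 28 ED50 as applying to 28 days of dosing.
- If the 3 mg group is not run, present the 10 mg data by day without a potency claim. Day 28 would then offer five points at one dose, and longer dosing would go with rising concentration.

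A repeat with AUC over 24 hours as the exposure measure is not proposed. As the 10 mg flow chart reads, the last PK sample on Day 28 is at 16:00, 7 hours after the 09:00 dose, so that AUC may not be well supported in that group.

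The cost is SAP wording and one more NLIN run on data already planned. The 10-point fit will be imprecise, so agreement between the two fits is reassurance, not proof of plateau.

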7.2 NULL AND ALTERNATIVE HYPOTHESES

It is not planned to test any statistical hypothesis with regard to the primary and secondary endpoints in a confirmatory sense. Instead, they will be described in their entirety and evaluated by descriptive statistical methods.

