7.4 INTERIM ANALYSES

No formal interim analysis is planned, however a preliminary analysis of MAO-B inhibition after completion of the 10 mg dose group will be performed.

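### The exploratory Emax fit caps only its starting values at 100%, so it can report a maximum above 100%, and it is to be fitted even if the trial ends after the 10 mg group for lack of inhibition

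*SAP*

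**What the plan says.** SAP section 7.4.2 states: "An Emax model will be fitted for plasma concentration against % reduction of MAO-B availability". E0 is fixed at 0. Emax, ED50 and the Hill factor are estimated with PROC NLIN (Marquardt) on the PKS, and the result is also plotted.

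The starting value for Emax is the largest observed % reduction, moved by 2.5 and 5 points either way "to get a range of starting values (values above 100 will be set to 100". This is the only place in the visible SAP where 100 acts as a limit. The printed code consists of PARAMETERS, MODEL and RUN statements. Its grid line, "PARAMETERS IMAX = imax.-5 to imax.+5 by 2.5", carries no cap, and there is no BOUNDS statement.

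Protocol section 1.3 says that the 10 mg group goes first and that "in the event no MAO-B inhibition is seen in this dose group, the study will be considered complete". Section 3.1 repeats this: "In case no MAO-B inhibition is seen in this dose group, the 3 mg dose group will not be further investigated". Section 7.4 adds that "a preliminary analysis of MAO-B inhibition after completion of the 10 mg dose group will be performed". The SAP (version 1, 17 January 2020) postdates the amendment of 24 June 2019 that introduced this decision point. Its visible text nevertheless describes both groups throughout and makes no exception to the fit. SAP section 6.6, on missing data, covers safety data, AE dates and PK, but not this model.

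**The concern.** A capped starting value does not cap an estimate: an unbounded least-squares search can leave the starting range in any direction. The planned data are 5 + 5 subjects with two post-dose scans each, so at most 20 points at two doses for three parameters. If the points do not show a plateau, Emax and ED50 trade off against each other. The plan followed as written could then report a maximum reduction that is physically impossible, with an ED50 that is too high. An inflated ED50 overstates the concentration needed for half-maximal brain MAO-B inhibition. In a trial meant to exclude clinical relevance, that errs towards reassurance.

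The second issue is simpler. If no inhibition is seen at 10 mg, the data are ten points scattered around zero from one dose. The model then has no effect to describe, and any Emax, ED50 and Hill factor it returns are noise.

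**Working it through.** The plan gives no figure to reproduce here: no power, precision or expected parameter value is stated. The check therefore has a part that needs no assumptions and a part that does.

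**Without assumptions**

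1. % reduction = 100 × (1 − post-dose availability / baseline availability). A value above 100 requires negative post-dose availability.
2. Starting grid: 5 Emax × 5 ED50 × 4 Hill values = 100 points. With an observed maximum of 98, the prose gives Emax starts of 93, 95.5, 98, 100, 100; the code gives 93, 95.5, 98, 100.5, 103. The cap acts only when the observed maximum exceeds 95. Neither version limits the final estimate.
3. Why ED50 follows Emax: with Hill 1, a curve through reduction R at concentration C has ED50 = C × (Emax − R)/R. As an illustration, take R = 50 at C = 1. Emax 90 gives (90 − 50)/50 = 0.8; Emax 100 gives 1.0; Emax 120 gives 1.4.

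**With assumptions** (none comes from the documents except the design of 5 + 5 subjects and two post-dose scans)

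The inputs were: exposure ratio between groups 3.3 or 6.4; concentration CV 40% between and 15% within subjects; residual SD 5 or 10 points with within-subject correlation 0.5; true Emax 70 or 90; Hill 1 or 2. That is 2 × 2 × 2 × 2 = 16 settings, with 500 trials each at mid-exposure and 150 each elsewhere. As written means the prose grid capped at 100, then an unbounded Marquardt search.

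| True ED50 | Emax above 100, all fits | Converged and Emax above 100 |
|---|---|---|
| mid-exposure | 1–42% (Hill 1: 17–42%; Hill 2: 1–31%) | 1–31% |
| quarter of mid-exposure | 0–48% | 0–23% |
| 4 × mid-exposure | 29–46% | 3–28% |

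At mid-exposure, 0–28% of fits did not converge. A separate, smaller simulation (true Emax 95, Hill 1, 60 replicates per scenario, so rough) gave Emax above 100 in about 13–52% with both groups.

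Estimated/true ED50, 10th to 90th percentile, at mid-exposure and exposure ratio 6.4 (converged fits as written; all fits when bounded):

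| Emax | Hill | SD | As written | Bounded |
|---|---|---|---|---|
| 90 | 1 | 5 | 0.65–2.51 | 0.65–1.37 |
| 90 | 1 | 10 | 0.47–3.97 | 0.49–1.49 |
| 90 | 2 | 5 | 0.86–1.18 | 0.86–1.17 |
| 90 | 2 | 10 | 0.77–1.54 | 0.77–1.27 |
| 70 | 1 | 5 | 0.57–2.92 | 0.57–2.59 |
| 70 | 1 | 10 | 0.45–4.63 | 0.48–3.02 |
| 70 | 2 | 5 | 0.82–1.27 | 0.82–1.27 |
| 70 | 2 | 10 | 0.67–1.89 | 0.67–1.72 |

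**10 mg group only, no true inhibition** (10 points)

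In the smaller simulation, at residual SD 3, 6 and 10, 50%, 38% and 33% of fits did not converge. A further 27%, 33% and 37% converged with a negative Emax, ED50 or Hill factor. Together these are 77%, 71% and 70% unusable. Non-convergence alone depends strongly on the optimiser: other runs under three tolerance and iteration settings gave 5–39%. None of these runs used PROC NLIN.

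**The case against.** **Importance.** The fit is exploratory. Protocol section 7.2 says: "It is not planned to test any statistical hypothesis with regard to the primary and secondary endpoints in a confirmatory sense". A reader might infer that the primary result is at risk. It is not: SAP section 7.4.1 is descriptive, by dose group, and works with one group or two. This stands, and it keeps the point minor.

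**Noise form.** If availability cannot be negative, no observation can exceed 100, and noise added in percentage points overstates the risk. This stands in part. With noise on the post-dose/baseline ratio, one check gave Emax above 100 in 6–32% (Hill 1) and 0–15% (Hill 2) of fits; another gave 1–40% overall. The risk shrinks in some settings but does not go away.

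**Mechanism.** Protocol section 3.2 raises irreversible inhibition that may accumulate, with time-dependent kinetics. A direct concentration–effect curve may then be the wrong model, and a true ED50 has no clear meaning. This stands as a limit on the ED50 ratios above, and the bound does not address it.

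**The bound is a trade-off.** An unbounded Emax above 100 shows visibly that no plateau was reached; a value held at 100 can look plausible. That is fair, and it is why an estimate on a bound must be declared. At mid-exposure the bound did not widen the ED50 spread in any setting tabulated.

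**Scope.** Rules for failed fits may exist in the ADS plan or in sponsor standards, which were not available. A reader might infer that the sponsor has no such rule; only the visible SAP supports that. By January 2020 the decision on the 3 mg group may also already have been taken, which would make the one-group case moot; the documents do not say. A reader might also expect misleading standard errors, because each subject's two scans share one baseline, but the SAP plans none for this fit.

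**Conclusion.** The point holds as a minor one about an exploratory analysis. On the text alone, the SAP uses 100% as a limit for starting values but not for the estimate, and it orders the fit even where the protocol's own stopping condition leaves no effect to model.

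The size rests on assumed inputs. Emax exceeds 100% in about 1–42% of fits when ED50 lies at mid-exposure. Bounding matters most at Hill 1 with a high true Emax: at Emax 90 and SD 5, the 90th percentile of estimated/true ED50 falls from 2.51 to 1.37. It matters little or not at all at Hill 2 with SD 5. These figures show what can happen; they do not predict this trial's data.

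In a 10 mg-only trial without inhibition most fits would be unusable, but no single non-convergence rate can be defended. The argument there does not need one: with no inhibition there is no ED50 to estimate.

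**What to change.** In SAP section 7.4.2:

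- Add `BOUNDS 0 < IMAX <= 100, IC50 > 0, HILL > 0;` to the PROC NLIN step.
- State in the output when an estimate sits on a bound, and that the plateau is then not identified.
- Report an ED50 outside the observed concentrations, flagged as extrapolated. Withholding it would remove too much: at mid-exposure this occurs in 0–35% of fits as written and 0–13% bounded, but in 27–83% of bounded fits when ED50 is a quarter of mid-exposure.
- If only the 10 mg group is run for lack of inhibition, or if the fit does not converge, show only the scatter plot of % reduction against concentration.

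Capping the printed Emax grid at 100 to match the prose is a tidy-up.

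The cost is one line of code and a few sentences, with no new data and no change to any endpoint or descriptive summary. The downsides are real. At mid-exposure 1–43% of fits sit on the bound, and Emax and ED50 will sometimes not be reported. The bound does not make the parameters identifiable: with ED50 at 4 times mid-exposure, the median bounded ED50 is still 0.52–0.98 of the true value.
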